8.3 LOST TO FOLLOW-UP

At any point during the trial, if a subject fails to return for a scheduled visit and is unable to be contacted by the site staff as outlined below, he or she will be considered lost to follow-up. This does not include a single missed visit of which the site was notified or a missed visit with subsequent contact from the subject, indicating an intention to continue on the study.

The following actions should be taken if a subject fails to return to the clinic for a required study visit:

- The site will attempt to contact the subject and reschedule the missed visit within the visit window and counsel the subject on the importance of maintaining the assigned visit schedule and ascertain if the subject wishes to and/or should continue in the study
- Before a subject is deemed lost to follow-up, the investigator or designee will make every effort to regain contact with the subject (where possible, 3 telephone calls). These contact attempts should be documented in the subject's medical record or study file
- Should the subject continue to be unreachable, he or she will be considered to have withdrawn from the study with a primary reason of lost to follow-up

9 STUDY ASSESSMENTS AND PROCEDURES

9.1 CLINICAL ASSESSMENTS

[REDACTED]

All ocular assessments will be conducted individually on both eyes in Part 1 (Dose Escalation) and on all Qualifying Eyes in Part 2 (Optional Dose Expansion), unless noted otherwise. Refer to the SoA (Section 1.3) to determine at which visits these assessments will be performed.

- **Vital sign measurements.** Vital signs (heart rate and blood pressure) will be taken after the subject has been in a seated position for at least 5 minutes. Height and weight will also be collected at the Baseline visit.
- **[REDACTED] dry eye disease symptom visual analog scale.** A VAS [REDACTED] will be completed by the subject for each eye individually, if applicable. The subject will rate each [REDACTED] symptoms by placing a single vertical mark on a horizontal line based on the extent of their symptoms. For each parameter, subjects will be asked to rate their discomfort from 0 (no discomfort) to 100 (maximal discomfort)

- [REDACTED]

- [REDACTED]

- [REDACTED]

- **Noncontact pachymetry.** Central corneal thickness in both eyes of a subject will be measured using a noncontact corneal pachymeter
- **Endothelial cell count.** Endothelial cell density will be assessed using noncontact specular microscopy
- **Visual acuity.** Best-corrected visual acuity will be measured for each eye using an ETDRS chart as per the investigator's standard clinical practice and performed with best correction. Best-corrected visual acuity refraction must be used for all visual acuity assessments for the duration of the study. Subject must wear the same glasses/trial frame (if applicable) at each visit
- [REDACTED]
- **Slit lamp examination** [REDACTED] Biomicroscopy will be performed for each eye. Eye structures/surfaces to be assessed include, but are not limited to, eyelid, lashes, bulbar conjunctiva, cornea, anterior chamber, iris, and lens. All observations will be recorded. [REDACTED]
- [REDACTED]
- **Corneal fluorescein staining** [REDACTED] corneal fluorescein staining assessment will be performed using the NEI grading system to score each of 5 corneal zones on a 0 to 3 scale ([Appendix 13.2](#)). The cornea will be assessed under the slit lamp using a cobalt blue light source and a Wratten #12 filter as per the investigator's standard clinical practice. [REDACTED]
- [REDACTED]
- **Intraocular pressure.** All IOP measurements must be measured by Goldmann applanation or Tono-Pen tonometry as per the investigator's standard clinical practice. To minimize

confounding variables, every effort should be made to measure all IOP measurements for each subject by the same examiner using the same tonometer and approximately at the same time at all visits

- **Fundus examination.** A dilated fundus exam (using 1 drop of tropicamide 1%) consisting of the vitreous, optic nerve, macula, and peripheral retina will be conducted, and the structures will be graded as normal or abnormal
- 
- **Pharmacokinetic assessment.** Blood will be collected and sent for analysis (C_{max} , T_{max} , AUC) of single-dose and repeated-dose INV-102. A blood sample will be collected pre-dose and 5, 15, 30, 60, and 120 minutes post-dose. 
 Refer to the SRM for details on collecting and processing blood samples
- **Adverse events.** The subject will be queried for AEs at each study visit and all AEs will be recorded in the eCRFs, including severity, action taken, and relationship to the study drug

9.2 ADVERSE EVENTS AND SERIOUS ADVERSE EVENTS

9.2.1 DEFINITION OF ADVERSE EVENTS

An AE is any untoward medical occurrence in a subject or clinical investigation participant administered a pharmaceutical product and that does not necessarily have a causal relationship with this study drug. An AE can therefore be any unfavorable and unintended sign (including an abnormal laboratory finding), symptom, or disease temporally associated with the use of a medicinal (investigational) product, whether or not related to that product.

All AEs that occur following consent and through the final study visit will be collected on the appropriate AE eCRF. All AEs recorded after starting study drug with the investigational product are considered TEAEs.

9.2.2 DEFINITION OF SERIOUS ADVERSE EVENTS

An AE or suspected adverse reaction is considered “serious” if, in the view of either the investigator or Sponsor, it meets one or more of the following criteria/outcomes:

- Death
- Life-threatening

- Inpatient hospitalization or prolongation of existing hospitalization
- Persistent or significant incapacity or substantial disruption of the ability to conduct normal life functions
- Congenital anomaly/birth defect

Important medical events that may not result in death, be life-threatening, or require hospitalization may be considered serious when, based upon appropriate medical judgment, they may jeopardize the subject and may require medical or surgical intervention to prevent one of the outcomes listed in this definition.

The following events are not considered SAEs:

- Outpatient treatment that does not result in hospital admission
- Hospitalization that is elective or preplanned for a pre-existing condition unrelated to the study drug and has not worsened since the start of the study

9.2.3 CLASSIFICATION OF AN ADVERSE EVENT

9.2.3.1 SEVERITY OF EVENT

The following guidelines will be used to describe severity.

- **Mild:** Require minimal or no treatment and do not interfere with the subject's daily activities
- **Moderate:** Result in a low level of inconvenience or concern with the therapeutic measures. Moderate events may cause some interference with functioning
- **Severe:** Interrupt a subject's usual daily activity and may require systemic drug therapy or other treatment. Severe events are usually potentially life-threatening or incapacitating. Of note, the term "severe" does not necessarily equate to "serious"

9.2.3.2 RELATIONSHIP TO STUDY INTERVENTION

All AEs must have their relationship to study intervention assessed by the clinician who examines and evaluates the subject based on temporal relationship and the clinician's clinical judgment. The degree of certainty about causality will be graded using the categories below.

- **Probably related:** There is evidence to suggest a causal relationship, and the influence of other factors is unlikely. The clinical event occurs within a reasonable time after administration of the study intervention, is unlikely to be attributed to concurrent disease or other drugs or chemicals, and follows a clinically reasonable response on withdrawal
- **Possibly related:** There is some evidence to suggest a causal relationship (eg, the event occurred within a reasonable time after administration of the trial medication). However, other factors may have contributed to the event (eg, the subject's clinical condition, other concomitant events)
- **Not related:** The AE is considered to be completely independent of study drug administration, and/or evidence exists that the event is definitely related to another etiology

9.2.3.3 EXPECTEDNESS

The medical monitor, in conjunction with the Sponsor, will be responsible for determining whether an AE is expected or unexpected in accordance with the Investigator's Brochure. An AE will be considered unexpected if the nature, severity, or frequency of the event is not consistent with the risk information previously described for the study intervention.

9.2.4 TIME PERIOD AND FREQUENCY FOR EVENT ASSESSMENT AND FOLLOW-UP

The occurrence of an AE or SAE may come to the attention of study personnel during study visits and interviews of a subject presenting for medical care or upon review by a study monitor.

All AEs, including local and systemic reactions not meeting the criteria for SAEs, will be captured on the appropriate eCRF. Information to be collected includes event description, date of onset, clinician's assessment of severity, relationship to study drug (assessed only by those with the training and authority to make a diagnosis), and date of resolution/stabilization of the event. All AEs occurring while on study must be documented appropriately regardless of relationship.

Any medical condition that is present at the time that the subject is screened will be considered as baseline and not reported as an AE. However, if the subject's condition deteriorates at any time during the study, it will be recorded as an AE.

Changes in the severity of an AE will be documented to allow an assessment of the duration of the event at each level of severity to be performed. Adverse events characterized as intermittent require documentation of onset and duration of each episode.

Site staff will record all reportable events with start dates occurring any time after informed consent is obtained through the Follow-Up Visit. At each study visit, the investigator or designee will inquire about the occurrence of AE/SAEs since the last visit. All AEs will be followed for outcome information until resolution or stabilization or the subject's participation in the trial ends. All SAEs and those nonserious events assessed by the investigator as possibly or probably related to the study drug should continue to be followed even after the subject's participation in the trial is over. Such events should be followed until they resolve or until the investigator assesses them as "chronic" or "stable."

9.2.5 ADVERSE EVENT REPORTING

Any AE should be recorded on the appropriate eCRF. All SAEs that are drug-related and unexpected are to be reported to the governing IRB as required by the IRB, local regulations, and the governing health authorities.

9.2.6 SERIOUS ADVERSE EVENT REPORTING

The investigator will report any SAE, whether or not considered related to the study drug, to the Sponsor within 24 hours of its occurrence or of learning of its occurrence. Recurrent episodes or progression of the initial SAE must be reported to the Sponsor within 24 hours of the investigator receiving the information. The investigator must include an assessment of whether there is a reasonable possibility that the study drug caused the event. The investigator must promptly inform the IRB of the SAE if it is deemed related to study drug and unexpected. All SAEs will be followed until satisfactory

resolution or until the investigator deems the event to be chronic or the subject is stable. The investigator should supply the Sponsor and the IRB with any additional requested information (eg, autopsy reports and terminal medical reports).

Adverse drug reactions that are both serious and unexpected (suspected unexpected serious adverse reactions [SUSARs]) will be subject to expedited reporting by the Sponsor to the United States Food and Drug Administration (FDA), as described in the Safety Plan. In addition, the Sponsor must notify FDA and all participating investigators in an Investigational New Drug (IND) safety report of potential serious risks, from clinical trials or any other source, as soon as possible, but in no case later than 15 calendar days after the Sponsor determines that the information qualifies for reporting.

9.2.7 REPORTING OF PREGNANCY

If a female subject becomes pregnant during the study, the investigator will notify the Sponsor (or its designee) and the medical monitor immediately after the pregnancy is confirmed and the female subject will be exited from the study. The investigator will (1) notify the subject's physician that the subject was being treated with INV-102 (or vehicle, as appropriate), and (2) follow the progress of the pregnancy to term and the health of the child to 12 months of age, providing written informed consent for release of this information. The investigator should document the outcome of the pregnancy and provide a copy of the documentation to the Sponsor.

10 STATISTICAL CONSIDERATIONS

10.1 SAMPLE SIZE DETERMINATION

Part 1 (Dose Escalation): The sample size of approximately 9 subjects each in Cohorts 1 to 4 (6 active: 3 vehicle) is considered sufficient for evaluation of safety, tolerability, and PK of each cohort. The sample size is not based on statistical power considerations.

Part 2 (Optional Dose Expansion): The sample size of approximately 48 subjects in Cohort 5 (32 active: 16 vehicle) is considered sufficient for evaluation of preliminary efficacy of INV-102. The sample size is not based on statistical power considerations.

10.2 POPULATIONS FOR ANALYSES

Three analysis populations will be defined and used in the statistical analyses: (1) a safety population, (2) a modified intent-to-treat (mITT) population, and (3) a per protocol (PP) population. Separate analysis populations will be defined in each part of the study.

Safety population: The safety population will include all randomized subjects who received at least 1 drop of study drug. The safety population will be used to summarize safety variables, using the study drug they actually received.

Modified intent-to-treat population: The mITT population will include all randomized subjects who received at least 1 drop of study drug in the Study Eye and completed at least 1 scheduled post-dosing assessment in the Study Eye. The mITT population will be used to analyze all efficacy endpoints, with subjects included in their randomized study drug regardless of the study drug they actually received. The Study Eye is defined as the eye with more severe disease based on corneal fluorescein staining. The other eye is designated as the Fellow Eye. If both eyes have the same corneal fluorescein staining score, the eye with the more severe eye dryness score from the [REDACTED] DED symptom VAS will be the Study Eye. If both eyes have the same eye dryness score, the right eye will be the Study Eye.

Per protocol population: The PP population includes all subjects in the mITT population who have study drug compliance of $\geq 80\%$ as defined by [REDACTED] and have no major protocol deviations considered to have significant impact on study drug outcome. The PP population will be used to analyze selected efficacy endpoints.

10.3 STATISTICAL ANALYSES

10.3.1 GENERAL APPROACH

Eyes meeting the study-defined DED eligibility criteria will be deemed Qualifying Eyes and each subject may have either 1 or 2 Qualifying Eyes. All subjects, regardless of whether they receive study drug in one or both eyes, will have only one eye designated as the Study Eye. The Study Eye is defined as the eye with more severe disease based on corneal fluorescein staining. The other eye is designated as the Fellow Eye. If both eyes have the same corneal fluorescein staining score, the eye with the more severe eye dryness score from the [REDACTED] DED symptom VAS will be the Study Eye. If both eyes have the same eye dryness score, the right eye will be the Study Eye.

In Part 1 (Dose Escalation) Cohorts 1 to 4, both eyes will receive study drug regardless of whether both eyes meet the criteria as Qualifying Eyes, and study assessments will be performed for both eyes (unless noted otherwise). Safety data from each eye will be analyzed. Non-eye-specific safety data (AE data) will be collected and analyzed at the subject level, and eye-specific safety data and efficacy data will be collected and analyzed at the eye level (Study Eye and Fellow Eye).

In Part 2 (Optional Dose Expansion) Cohort 5, only eyes meeting DED eligibility (Qualifying Eyes) will receive study drug and be assessed. Safety data from only those eyes will be analyzed. Non-eye-specific safety data (AE data) will be collected and analyzed at the subject level, and eye-specific safety data and efficacy data will be collected and analyzed at the eye level (Study Eye and, if applicable, Fellow Eye).

The database will be locked after all subjects exit the study and all data clarification forms or queries have been resolved. Prior to database lock, a detailed SAP will be finalized and approved.

All continuous variables will be summarized by study drug and time point (as applicable) using descriptive statistics (n, mean, median, standard deviation, minimum, and maximum). All categorical variables will be summarized by study drug and time point (as applicable) using frequency counts and percentages. Analysis of the efficacy endpoints will be based on the mITT population and safety endpoints will be based on the safety population unless otherwise specified.

Safety and efficacy endpoint results will be presented separately for Part 1 (Dose Escalation) and Part 2 (Optional Dose Expansion). [REDACTED]

All study data will be presented by study drug and time point (as applicable).

All statistical tests will be performed using a significance level of 5% (2-tailed). The p-values for the analysis of efficacy endpoints will be considered descriptive.

10.3.2 ANALYSIS OF THE PRIMARY EFFICACY ENDPOINT

For Part 2 (Optional Dose Expansion), the primary efficacy endpoint is the change from Baseline to Day 15 in either eye dryness VAS score OR eye discomfort VAS score from the [REDACTED] DED symptom VAS, [REDACTED] based on results from Part 1 (Dose Escalation) Cohorts 1 to 4.

The change in VAS score will be analyzed using a mixed model for repeated measures (MMRM) that includes treatment (INV-102 or vehicle), visit (Days 8 and 15), and treatment-by-visit interaction terms and Baseline as a covariate. The least squares (LS) mean and 95% confidence interval (CI) for each study drug group, the LS mean difference between study drug groups, and the associated p-value and 95% CI for the mean difference will be presented at each visit. Sensitivity analyses may be performed imputing missing data. Full details will be provided in the SAP.

The primary efficacy analyses will be conducted on the mITT and PP populations.

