10.3.3 ANALYSIS OF THE SECONDARY AND OTHER EFFICACY ENDPOINTS

All secondary and other efficacy analyses will be conducted on the mITT population, and select analyses on the PP population, using the following efficacy variables [REDACTED]

- Eye Dryness Composite Score (combines the change in eye dryness score from the [REDACTED] DED symptom VAS plus the change in corneal fluorescein staining)

- Eye Discomfort Composite Score (combines the change in eye discomfort score from the [REDACTED] DED symptom VAS plus the change in corneal fluorescein staining)
- Changes in VAS (individual item scores and overall score [sum [REDACTED]
- [REDACTED]
- Changes in corneal fluorescein staining [REDACTED]
- [REDACTED]
- [REDACTED]
- [REDACTED]
- [REDACTED]

The Eye Dryness Composite Score and the Eye Discomfort Composite Score will each be a combination score of the VAS (either the "eye dryness score" or the "eye discomfort score") change from Baseline and corneal fluorescein staining change from Baseline using the following equation:

$$\text{[REDACTED]}$$

Endpoints in Part 1 (Dose Escalation) will be summarized descriptively at each visit, showing actual values and change from Baseline values.

For Part 2 (Optional Dose Expansion), continuous endpoints measured over multiple visits will be analyzed using MMRM that include treatment, visit, and treatment-by-visit interaction terms and Baseline as a covariate.

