### Primary endpoint

- Change from Baseline to Day 15 in the Eye Dryness Score from the [REDACTED] DED symptom VAS

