### **7.2. Covariates and Subgroups**

#### **7.2.1. Planned Covariates**

Planned covariates include baseline values for the given assessment.

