### 9.1. Primary Efficacy

The primary efficacy endpoint to be used in Part 2 was [REDACTED]  
[REDACTED] the Change from Baseline to Day 15 in the Eye Dryness Score from the [REDACTED] DED symptom VAS.

[REDACTED]  
[REDACTED]  
[REDACTED]  
[REDACTED]  
[REDACTED]

For Part 2 (Cohort 5), the primary efficacy endpoint, which is measured over multiple visits, will be summarized [REDACTED]. In addition, the Part 2 data will be analyzed using a mixed model for repeated measures (MMRM) that include treatment, visit, and treatment-by-visit interaction terms, and baseline eye dryness or eye discomfort VAS score as a covariate. The output from the MMRM will include the least-squares mean (LSM) and standard error for both treatment groups, along with the vehicle-corrected LSM, its 95% CI, and associated p-value. Include the average of study eye and fellow eye. LS mean values will also be displayed by visit and treatment group using line graphs.

[REDACTED]  
[REDACTED]  
[REDACTED]  
[REDACTED]

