### 9.2. Secondary and Other Efficacy

Secondary and other efficacy endpoints are indicated in Section 4.1. [REDACTED]  
[REDACTED]  
[REDACTED]  
[REDACTED]  
[REDACTED]  
[REDACTED]  
[REDACTED]

Secondary and other efficacy data in Part 2 will be summarized [REDACTED]. In addition, Part 2 data will be analyzed using a similar MMRM as for the primary endpoint, with change from baseline as the dependent variable, treatment as factor, and the respective baseline value included as the covariate. The output from each MMRM will include the LSM and standard error for both treatment groups, along with the vehicle-corrected LSM, its 95% CI, and associated p-value.

[REDACTED]  
[REDACTED]  
[REDACTED]

If there are sufficient missing data, appropriate MI methods will be applied as described in Section 7.3.2.3.

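### The Part 2 MMRM has no baseline-by-visit term, so the Day 15 primary contrast is adjusted with a baseline slope pooled over visits rather than its own

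*Protocol*

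**What the plan says.** The Part 2 primary endpoint is the "Change from Baseline to Day 15 in the Eye Dryness Score from the" DED symptom VAS (SAP 4.1). Protocol 10.3.2 models it with treatment, "visit (Days 8 and 15), and treatment-by-visit interaction terms and Baseline as a covariate", and reports the LS mean difference with its 95% CI at each visit. SAP 9.1 gives "treatment, visit, and treatment-by-visit interaction terms, and baseline eye dryness or eye discomfort VAS score as a covariate", without listing the visits.

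For the other continuous Part 2 endpoints, Protocol 10.3.3 specifies "MMRM that include treatment, visit, and treatment-by-visit interaction terms and Baseline as a covariate". SAP 9.2 refers back to a similar model, with "treatment as factor, and the respective baseline value included as the covariate". SAP 7.2.1 adds only this: "Planned covariates include baseline values for the given assessment".

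No visible text in either document includes a baseline-by-visit interaction. Some text around the SAP model paragraphs is blacked out, but the term lists in Protocol 10.3.2 and 10.3.3 and in SAP 9.1 are complete sentences.

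**The concern.** The model lets the treatment effect differ by visit but holds the relation of change to baseline equal at Day 8 and Day 15. That relation can change over time, for example if the correlation with baseline weakens. The endpoint of interest is Day 15 alone, yet its adjustment borrows from Day 8.

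With 32 versus 16 subjects, chance baseline differences between arms are not trivial. If the two visit slopes differ, the pooled slope removes somewhat too much or too little of such a difference from the Day 15 estimate. Part 2 has no power basis and its p-values are descriptive, so the point estimate and its CI are the main product. What is at stake is a modest shift in that one estimate and a small loss of precision.

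**Working it through.** The plan has no figure to reproduce, because the Part 2 sample size is not power-based.

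**Inputs.** From the documents: 32 active and 16 vehicle subjects; visits at Day 8 and Day 15 (Protocol 10.3.2); VAS scored 0 to 100. Assumed, because the documents give none: baseline SD s0 = 15–20; visit SDs s8 and s15 = 18–25; correlation with baseline c8 = 0.5–0.65 and c15 = 0.3–0.45; correlation between visits c = 0.7–0.75; complete data; unstructured residual covariance.

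**Formulas.**
- Slope of change on baseline at visit k: b_k = c_k × s_k / s0 − 1.
- Residual SD at visit k: e_k = s_k × √(1 − c_k²).
- Residual correlation: ρ = (c − c8·c15) / √[(1 − c8²)(1 − c15²)].
- Pooled slope: b = w8·b8 + (1 − w8)·b15, with w8 = (r² − ρr) / (1 + r² − 2ρr) and r = e15/e8.
- SD of the chance baseline difference: s0 × √(1/32 + 1/16) = 0.306·s0, which is 4.6 to 6.1 points.
- Shift in the Day 15 contrast at a 1-SD imbalance: w8 × |b15 − b8| × 0.306·s0. Since (b8 − b15)·s0 = c8·s8 − c15·s15, this equals 0.306 × w8 × |c8·s8 − c15·s15|, and the baseline SD cancels.
- Standard error of the Day 15 contrast: 0.306 × e15.

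**Three cases from the assumed ranges (s0 = 15).**

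| | A | B | C |
|---|---|---|---|
| s8, s15 | 18, 20 | 20, 20 | 25, 25 |
| c8, c15, c | 0.50, 0.45, 0.70 | 0.55, 0.40, 0.70 | 0.65, 0.30, 0.75 |
| b8, b15 | −0.40, −0.40 | −0.27, −0.47 | 0.08, −0.50 |
| e8, e15 | 15.6, 17.9 | 16.7, 18.3 | 19.0, 23.8 |
| ρ, r | 0.61, 1.15 | 0.63, 1.10 | 0.77, 1.26 |
| w8 | 0.67 | 0.62 | 0.94 |
| c8·s8 − c15·s15 | 9 − 9 = 0 | 11 − 8 = 3 | 16.25 − 7.5 = 8.75 |
| Shift at 1 SD | 0 | 0.306 × 0.62 × 3 = 0.57 | 0.306 × 0.94 × 8.75 = 2.5 |
| Standard error | 5.5 | 5.6 | 7.3 |

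In case A the rising SD exactly offsets the falling correlation, so the slopes agree and nothing shifts. Case C is the extreme of the assumed ranges.

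**Precision.** To first order, the variance with the pooled slope relative to a visit-specific slope is 1 + (shift/SE)². Case B gives 1 + (0.57/5.6)² = 1.01. Case C gives 1 + (2.5/7.3)² = 1.12, before the cost of estimating a second slope. In simulation at 32 versus 16, adding the term changed the Day 15 variance by between about a 0.5% loss and a 10% gain. In a separate simulation (baseline SD 15, Day 8 residual SD 18, ρ = 0.6, slopes −0.3 and −0.5, covariance taken as known, complete data), the mean contrasts from the two models agreed within 0.04 points. The empirical SDs, pooled versus separate, were 5.50 versus 5.47 at r = 1.0 and 6.62 versus 6.55 at r = 1.2.

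**Where the pooled slope leans.** With equal residual SDs, w8 is exactly 0.50 for any ρ; compound symmetry or AR(1) would impose this. At ρ = 0.6, w8 is 0.62, 0.72 and 0.81 for r = 1.1, 1.2 and 1.3, but 0.37 and 0.24 for r = 0.9 and 0.8. With equal SDs and 20% missing at Day 15, the simulated weight is about 0.53.

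**The case against.** A baseline main effect is a valid specification, and the protocol and SAP agree on it. Randomization makes the expected baseline difference zero, so the treatment estimate is unbiased over repeated trials. The sample size is not power-based and efficacy p-values are descriptive. The precision gain can be nil. All of this stands, and it is why the point is an optional improvement.

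Two stronger readings are tempting, and the documents support neither.

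- A reader might infer that Day 15 is adjusted mainly with the Day 8 slope. That holds only if the Day 15 residual variance is larger. There is an argument for it: if the visit SDs are equal and correlation with baseline falls, the Day 15 residual SD must rise, and the assumed ranges then give a Day 8 weight of 0.54 to 0.94. But equal residual variances give an even split, a smaller Day 15 variance tips the weight to Day 15, and the documents do not show which applies.
- A reader might infer that the estimate is biased, or that the shared slope must be wrong. Case A shows the slopes can coincide. Where they differ, the consequence is a conditional shift that also needs a chance baseline imbalance.

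The redactions near the SAP model also call for some caution, although the visible term lists leave little room for a further fixed effect.

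**Conclusion.** The point holds as a small refinement. As written, the Part 2 MMRM adjusts the Day 15 contrast with a slope pooled over visits. The realized estimate then shifts by about 0 to 2.5 points per 1 SD of chance baseline imbalance, typically under 1 point, against a standard error of about 5 to 7 points. The upper end requires correlation with baseline to fall from 0.65 to 0.30 within a week. These sizes rest wholly on assumed SDs and correlations, on complete data and on two modelled visits. If the visit term in the SAP also covers Day 22, the slope is pooled over three visits, which this calculation does not cover.

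**What to change.** Add a baseline-by-visit interaction to the Part 2 MMRM in Protocol 10.3.2 and 10.3.3 and SAP 9.1 and 9.2, and report the Day 15 LS mean difference from that model. SAP 9.1 should also name the modelled visits. The residual covariance structure should be stated too, unless it already stands in the blacked-out text, because it affects how the pooled slope is weighted.

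The cost is one model term in wording and code. It uses one degree of freedom with two visits, or two if Day 22 is modelled, and loses a negligible amount of precision if the slopes are in fact equal. No new data are needed and the estimand does not change. The change should be made before the Part 2 assignments are unmasked.
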